6.5.3.4 Reasons for vaccination discontinuation and early study termination

The number and percentage of participants who discontinue vaccination and who terminate the study early will be tabulated by reason and treatment arm (Part B).

6.5.4 Immunogenicity analysis

6.5.4.1 General approach

For the statistical analysis of immunogenicity endpoints, data from enrolled participants in Part B will be used according to the initial randomization assignment regardless of how many injections the participants received. Additional analyses may be performed, limited to participants who received all scheduled injections per protocol. Assay results from specimens collected outside of the visit window, or from HIV-infected participants collected post infection, may be excluded. Since the exact date of HIV infection is unknown, any assay data from blood draws 4 weeks prior to an infected participant's last seronegative

sample and thereafter may be excluded. If an HIV-infected participant does not have a seronegative sample post enrollment, then all data from that participant may be excluded from the analysis.

Discrete categorical assay endpoints (eg, response rates) will be analyzed by tabulating the frequency of positive response for each assay by antigen and treatment arm at each timepoint for which an assessment is performed. Crude response rates will be presented with their corresponding 95% CI estimates calculated using the score test method (52). Barnard's or Fisher's exact tests, as specified in the SAP, will be used to compare the response rates of any 2 vaccine arms, with a significant difference declared if the 2-sided p-value is ≤ 0.05 . In general, Barnard's is preferred since, under most circumstances, it is more powerful than Fisher's (54).

In addition to response rate estimates for each timepoint, the probability of observing at least 1 positive response by a given timepoint and the probability of observing more than 1 positive response by a given timepoint will be estimated, with corresponding CIs, for each vaccine arm using maximum likelihood-based methods (55).

For quantitative assay data (eg, the vaccine-induced serum neutralizing antibody [nAb] as measured by the TZM-bl assay, HIV-specific serum IgG binding magnitude, breadth, and avidity to cross-clade panels of gp120 and V1V2 and to V3, CD4i, gp41 and gp41 immunodominant region [IDR] as assessed by the binding antibody multiplex assay [BAMA] or CD4+ T-cell responses to Gag and Env as assessed by ICS), graphical and tabular summaries of the distributions by antigen, treatment arm, and timepoint will be made. For all primary and secondary immunogenicity endpoints, box plots and plots of estimated reverse cumulative distribution curves will be used for graphical display of all of the study arms. Typically, the results will be shown for each vaccine arm.

The difference between arms at a specific timepoint will be tested with a nonparametric Wilcoxon rank sum test if the data are not normally distributed and with a 2-sample t-test if the data appear to be normally distributed. To test for differences among all vaccine arms, first a Kruskal-Wallis rank test or an F-test (depending on the normality assumption) will be used to test for overall differences. Secondly, if the overall test is significant at the 2-sided 0.05 level, then individual tests comparing between vaccine arms will be done. If rank-based tests are used, then the tests will be inverted to construct Hodges-Lehmann point estimates and 2-sided $(1-0.05/\# \text{ of comparisons}) \times 100\%$ CIs about the differences in location centers of the number of comparisons between vaccine arms. If rank-based tests are used, then the tests will be inverted to construct Hodges-Lehmann point estimates and 2-sided $(1-0.05/\# \text{ of comparisons}) \times 100\%$ CIs about the differences in location centers of the number of comparisons between vaccine arms. When all pair-wise comparisons between the multiple vaccine arms are of interest, the Tukey procedure (56) will be used. If only specific comparisons

between pairs of the multiple vaccine arms are of interest, the Holm-Bonferroni procedure will be used. An appropriate data transformation (eg, log10 transformation) may be applied to better satisfy assumptions of symmetry and homoscedasticity (constant variance). Significance of the differences between pairs will be evaluated using 2 procedures, first based on whether the simultaneous 95% CIs exclude zero and secondly, based on whether the nominal (unadjusted) 95% CIs exclude zero.

Some immunologic assays have underlying continuous or count-type readout that are dichotomized into responder/nonresponder categories (eg, nAb, BAMA, ICS). If treatment arm differences for these assays are best summarized by a mixture model, then either Lachenbruch's test statistic (57) or an alternative 2-part test (58) (as defined in the SAP) will be used to evaluate the composite null hypothesis of equal response rates in the 2 arms and equal response distributions. Lachenbruch's test statistic equals the square of a binomial Z-statistic for comparing the response rates plus the square of a Wilcoxon statistic for comparing the response distributions in the subgroup of responders. A permutation procedure is used to obtain a 2-sided p-value. For estimation, differences in response rates between arms will be estimated using the methods described above, and in the subgroup of positive responders, differences in location parameters between arms will be estimated using the methods described above.

More sophisticated analyses employing repeated measures methodology (for example, linear mixed models or marginal mean models fit by generalized estimating equations [GEE]) may be utilized to incorporate immune responses over several timepoints and to test for differences over time. However, inference from such analyses would be limited by the small sample size of this study. All statistical tests will be 2-sided and will be considered statistically significant if $p \leq 0.05$.

Based upon previous HVTN trials, missing 15% of immunogenicity results for a specific assay is common due to study participants terminating from the study early, problems in shipping specimens, or low cell viability of processed PBMCS. To achieve unbiased statistical estimation and inferences with standard methods applied in a complete-case manner (only including participants with observed data in the analysis), missing data need to be missing completely at random (MCAR). Following the most commonly used definition, MCAR assumes that the probability of an observation being missing does not depend on any participant characteristics (observed or unobserved). When missing data are minimal (specifically if no more than 20% of participants are missing any values), then standard complete-case methods will be used, because violations of the MCAR assumption will have little impact on the estimates and hypothesis tests.

If a substantial amount of immunogenicity data are missing for an endpoint (at least 1 value missing from more than 20% of participants), then using the methods

that require the MCAR assumption may give misleading results. In this situation, analyses of the immunogenicity endpoints at a specific timepoint will be performed using parametric generalized linear models fit by maximum likelihood. These methods provide unbiased estimation and inferences under the parametric modeling assumptions and the assumption that the missing data are missing at random (MAR). MAR assumes that the probability of an observation being missing may depend upon the observed responses and upon observed covariates, but not upon any unobserved factors. Generalized linear models for response rates will use a binomial error distribution and for quantitative endpoints, a normal error distribution. For assessing repeated immunogenicity measurement, linear mixed effects models will be used. If the immunological outcomes are left- and/or right-censored, then the linear mixed effects models of Hughes (59) will be used because they accommodate the censoring. In addition, secondary analyses of repeated immunogenicity measurements may be done using weighted GEE (60) methods, which are valid under MAR. All of the models described above in this paragraph will include as covariates all available baseline predictors of the missing outcomes.

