6.2.1 Sample size calculations for immunogenicity

The main goals of this trial regarding immunogenicity outcomes involve assessing the ability of FP-conjugate and Trimer 4571 vaccines alone or co-administration to elicit antibody binding FP and envelop trimer antigens and mapping FP-specific serum neutralizing activity induced by the prime vaccines regimens in Groups 5-8 and prime boost vaccines regimens in Groups 7-8. No adjustment for multiple comparisons will be made for the use of multiple assays. The precision with which the true response rate can be estimated from the observed data depends on the true underlying response rate and the sample size. Two-sided 95% CIs for the response rate based on observing a particular rate of responses in the vaccinees is shown in [Table 6-3](#). Calculations are done using the score test method (52). The sample size of n = 13 (Groups 5-6) and n=9 for each of Groups 7 and 8 will be used to evaluate the immunogenicity post the 1st vaccination induced by the vaccination; the sample sizes of n=4, 5 for Groups 7-8 will be used to evaluate the immunogenicity post the 2nd vaccination.

Table 6-3 Two-sided 95% confidence intervals for the true response rate based on observing a particular rate of responses in the vaccinees (n =4, 5, 9, 13)

No. of responses	Observed response rate (%)	95% Confidence interval
2/4	50	[15, 85]
4/4	100	[51, 100]
2/5	40	[11.8, 76.9]
4/5	80	[37.6, 96.4]
3/9	33.3	[12.1, 64.6]
6/9	66.7	[35.4, 87.9]
9/9	100	[70.1, 100]
3/13	23.1	[8.2, 50.3]
6/13	46.2	[23.2, 70.9]
9/13	69.2	[42.4, 87.3]

As shown in [Table 6-4](#), there is limited power for a formal comparison of immunogenicity response rates between Group 7 (n=9) and Group 8 (n=9). For either 80% or 90% power, the sizes of differences that the trial is powered to detect are fairly large. These calculations use a Fisher exact 2-sided test with a type I error rate of 0.05.

Table 6-4 Power for comparison of response rates between 2 arms (n1 = 9, n2 = 9)

True response rate Arm 1 (%)	Minimum true response rate in Arm 2 in order to detect a difference	
	80% power	90% power
10	83	91
20	92	99
30	99	

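### Table 6-4's detectable response rates match neither Barnard's test, which the Protocol prefers, nor exact Fisher's, and the supplied documents do not settle which test applies

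*Protocol*

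**What the plan says.** Protocol section 6.5.4.1 (General approach) sets the analysis rule for response rates: "Barnard's or Fisher's exact tests, as specified in the SAP, will be used to compare the response rates of any 2 vaccine arms". The threshold for calling two arms different is a two-sided p of 0.05 or less. On the choice between the tests, the section adds: "In general, Barnard's is preferred since, under most circumstances, it is more powerful than Fisher's".

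The SAP supplied with the Protocol is version 2.0. Its Overview limits it to safety data, for safety monitoring board reports and the final safety report. It mentions neither Barnard's nor Fisher's test.

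Protocol section 6.2.1 gives the planning figures for comparing Group 7 with Group 8 at 9 per arm. Of Table 6-4 it says: "These calculations use a Fisher exact 2-sided test with a type I error rate of 0.05". The table prints the minimum arm 2 response rate for 80%/90% power as 83/91 when arm 1 is at 10%, 92/99 at 20%, and 99/blank at 30%. For samples after the second dose, the section says "the sample sizes of n=4, 5 for Groups 7-8 will be used to evaluate the immunogenicity post the 2nd vaccination".

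Response rate is one part of primary endpoint 2 (section 3.1).

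**The concern.** The power table is computed for a test that the analysis section does not prefer, and the choice between the two tests is passed to a document that is not among those supplied. At 9 per arm the two tests have different rejection regions. Two things follow. A reader of section 6.2.1 gets a wrong picture of the differences the comparison can detect under the preferred test. Some possible results would also be declared significant or not according to which test is picked. The study is open-label to sites and participants, and section 6.5.5.2 allows analysis by arm before follow-up ends, so the choice should be fixed before the assay data are analysed.

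**Working it through.** **Inputs.** Arms of 9 and 9, two-sided alpha of 0.05, and the printed entries of Table 6-4 (all section 6.2.1); the rule p ≤ 0.05 and the two candidate tests (section 6.5.4.1).

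**Method.** Enumerate all 10 × 10 = 100 outcomes (a responders of 9 in one arm, b of 9 in the other) and compute both p-values for each. Let R be the set of outcomes with p ≤ 0.05. Power at true rates p1 and p2 is the sum over R of C(9,a) p1^a (1−p1)^(9−a) × C(9,b) p2^b (1−p2)^(9−b). Type I error is the same sum with p1 = p2, maximised over the common rate.

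**Step 1: reproduce the plan's own figure.** Exact Fisher's at 9 vs 9, smallest whole-percent arm 2 rate for 80%/90% power:

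| Arm 1 | Printed | Exact Fisher's | Barnard's |
|---|---|---|---|
| 10% | 83 / 91 | 78 / 86 | 74 / 82 |
| 20% | 92 / 99 | 89 / 94 | 85 / 91 |
| 30% | 99 / blank | 96 / 100 | 93 / 97 |

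The printed entries do not reproduce. Under exact Fisher's, the 80% entries have power of 86.8%, 86.9% and 88.5%, and the two filled 90% entries have 95.1% and 97.3%. A continuity-corrected normal formula at n = 9 needs 81.0/86.7, 90.9/95.9 and 98.7/none. That is close to the 80% column but not to the 90% column.

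**Step 2: split the gap between the printed entries and Barnard's.**
- Printed minus Barnard's: 83−74 = 9, 91−82 = 9, 92−85 = 7, 99−91 = 8, 99−93 = 6.
- Due to the choice of test (Fisher's minus Barnard's, including the cell left blank): 4, 4, 4, 3, 3, 3.
- Due to the table not reproducing under Fisher's (printed minus Fisher's): 5, 5, 3, 5, 3.

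**Step 3: verdicts that depend on the test.** Listing a < b only, Barnard's rejects for these outcomes:
- a = 0 with b = 4 to 9
- a = 1 with b = 6 to 9
- a = 2 with b = 7 to 9
- a = 3 with b = 8 or 9
- a = 4 or 5 with b = 9

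That is 6 + 4 + 3 + 2 + 1 + 1 = 17 outcomes, or 34 with mirror images. Fisher's drops 0 vs 4, 2 vs 7 and 5 vs 9, leaving 14, or 28 with mirrors. Six outcomes therefore change verdict, all from non-significant (Fisher's) to significant (Barnard's).
- 0/9 vs 4/9: Fisher p = 2 × C(9,4)/C(18,4) = 2 × 126/3060 = 0.082; Barnard p = 0.033. The result 5/9 vs 9/9 is its complement and has the same p-values.
- 2/9 vs 7/9: Fisher p = 2 × (36×36 + 9×9 + 1)/C(18,9) = 2 × 1378/48620 = 0.057; Barnard p = 0.031.

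Pooled and unpooled versions of Barnard's statistic give the same six.

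**Step 4: type I error.** For Barnard's the maximum is at a common rate of 0.5. Summing C(9,a)C(9,b) over the 17 outcomes gives 382 + 1170 + 1656 + 840 + 126 + 126 = 4300, and 2 × 4300/2^18 = 8600/262144 = 3.3%. For Fisher's the maximum is 2.1%.

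**Step 5: power, Fisher's vs Barnard's.**

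| True rates | Fisher's | Barnard's | Loss (points) |
|---|---|---|---|
| 10% vs 83% | 86.8% | 92.0% | 5.2 |
| 20% vs 92% | 86.9% | 91.5% | 4.7 |
| 30% vs 99% | 88.5% | 95.3% | 6.8 |
| 10% vs 91% | 95.1% | 97.8% | 2.7 |
| 20% vs 99% | 97.3% | 98.9% | 1.6 |
| 10% vs 60% | 48.6% | 57.9% | 9.3 |
| 20% vs 80% | 62.5% | 72.1% | 9.6 |

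Losses are computed before rounding. The loss depends on the rates: it is near zero at 10% vs 100% and about 25 points at 50% vs 100%.

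**Step 6: other sizes.** At 4 vs 5 (after the second dose) no outcome changes verdict. At 10 vs 9, eight do.

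**The case against.** A reader might infer that sections 6.2.1 and 6.5.4.1 contradict each other about which test decides the comparison. The documents do not support that. Section 6.2.1 names Fisher's only for the calculations behind Table 6-4, and 6.5.4.1 alone sets the decision rule. Planning on a conservative test and analysing with a more powerful one is ordinary practice.

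A reader might also credit the whole 6 to 9 point gap in Table 6-4 to the choice of test. Step 2 shows that the test accounts for 3 to 4 points. A single unqualified figure for the power loss would mislead too, because the loss varies widely with the true rates.

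The strongest defence is that the choice may already be made elsewhere. The Protocol also defers other immunogenicity details to a SAP, such as the two-part test and the positivity criteria, and the safety SAP contains none of them. A separate immunogenicity SAP is plausible, so silence in a safety SAP does not show that the test is unspecified. This stands, and it is why the open choice alone would be only a small point.

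The stakes are also limited. Primary objective 2 asks whether the vaccines elicit binding antibodies and specifies no comparison between arms; comparing regimens falls under exploratory objective 3. The score confidence intervals for response rates do not depend on this choice. Section 6.2.1 already warns that power is limited, and the printed table errs on the cautious side.

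None of this rescues Table 6-4. Whichever exact test a SAP names, the printed entries do not match it.

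**Conclusion.** The point holds for Table 6-4 and, more modestly, for the unsettled choice of test. The printed minimum detectable rates exceed those of the preferred test by 6 to 9 points, and those of exact Fisher's by 3 to 5. The cell left blank is reachable at 97% under Barnard's and only at 100% under Fisher's. Fixing the test matters for six of the 100 outcomes at 9 vs 9. Fisher's gives up about 5 to 7 points of power at the table's 80% entries, 2 to 3 at its 90% entries, and 9 to 10 at pairs such as 10% vs 60% or 20% vs 80%. Moving to Barnard's does not threaten error control, with maxima of 3.3% against 2.1%.

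This rests on independent binomial responses, 9 evaluable participants per arm as section 6.2.1 states, and two-sided p ≤ 0.05. The count of six outcomes assigns them no probability of occurring. Whether an immunogenicity SAP has already settled the test cannot be determined from the documents supplied.

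**What to change.** In section 6.5.4.1, before assay data are analysed, replace the either/or wording with Barnard's two-sided unconditional exact test for response-rate comparisons, and state the test statistic. This follows the Protocol's own preference. In section 6.2.1, name the same test and restate Table 6-4 as 74/82 (arm 1 at 10%), 85/91 (20%) and 93/97 (30%). If the immunogenicity SAP specifies Fisher's instead, cite it in 6.5.4.1 and restate the table as 78/86, 89/94 and 96/100.

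The cost is one sentence and one recomputed table. It needs no new data or samples, and type I error at 9 vs 9 stays below 5% either way.

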HIV VACCINE
TRIALS NETWORK

PROTOCOL

HVTN 303

A Phase 1, Open-Label Clinical Trial to Evaluate Safety, Tolerability, and Immunogenicity of Adjuvanted HIV-1 Fusion Peptide Conjugate Vaccine (VRC-HIVVCP0108-00-VP) Alone or in Prime-Boost Regimens with Adjuvanted HIV-1 Envelope Trimer 4571 (VRC-HIVRGP096-00-VP) and HIV-1 Trimer 6931 (VRC-HIVRGP0106-00-VP) Vaccines in Healthy Adults

DAIDS DOCUMENT ID 38835

IND 028412 HELD BY DAIDS

CLINICAL TRIAL SPONSORED BY

Division of AIDS (DAIDS)
National Institute of Allergy and Infectious Diseases (NIAID)
National Institutes of Health (NIH)
Department of Health and Human Services (DHHS)
Bethesda, Maryland, USA

STUDY PRODUCTS PROVIDED BY

Vaccine Research Center (VRC)
NIAID, NIH, DHHS
Bethesda, Maryland, USA

September 21, 2023

Final
HVTN 303
Version 2.0

HVTN 303 enrolled (vaccinated) its first participant on August 15, 2022, with the goal to enroll 60 participants in the study. As of Dec 20, 2022, 44 participants were enrolled (no enrollments occurred after this date). Part A (Groups 1, 2, 3, 4, and 5) completed enrollment of 15 participants from August 15 to October 14, 2022.

Part B enrolled 29 participants from November 3 to December 20, 2022: Group 6 enrolled 10 ppts, all of whom received 1 vaccination; Group 7 enrolled 10 participants, 5 of whom received 2 vaccinations; Group 8 enrolled 9 participants, 6 of whom received 2 vaccinations. No participants received a 3rd vaccination.

Over time, the PSRT observed trends in local and systemic reactogenicity (grade 3 fever, grade 3 injection site erythema, and/or induration/swelling), unsolicited adverse events (urticaria, rash, and serum sickness), and temporary increases in absolute eosinophil counts (AECs) post-vaccination. Certain of these events resulted in pauses in all vaccinations, and the PSRT requested the HVTN Safety Monitoring Board (SMB) perform an ad hoc review of all safety data. Following this review on January 11, 2023, the SMB recommended that all vaccinations in the study be permanently discontinued, and that participants be continued in safety follow-up, and these recommendations were implemented.

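### The fallback for more than 20% missing fits response rates by maximum-likelihood binomial regression and has no rule for an arm with 0% or 100% responders

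*Protocol*

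**What the plan says.** Protocol section 6.5.4.1 (General approach) has two routes for response rates. With little missing data, crude rates get score confidence intervals and arms are compared by Barnard's or Fisher's exact test. All of these are defined at 0% and 100%.

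The second route starts when there is "at least 1 value missing from more than 20% of participants". Then "analyses of the immunogenicity endpoints at a specific timepoint will be performed using parametric generalized linear models fit by maximum likelihood". For binary endpoints, "Generalized linear models for response rates will use a binomial error distribution". On covariates, "All of the models described above in this paragraph will include as covariates all available baseline predictors of the missing outcomes". On properties, "These methods provide unbiased estimation and inferences under the parametric modeling assumptions", together with missingness at random.

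The section does not name the link function, the type of test or interval, or what to do if an arm is all responders or all non-responders. It does not say whether the score interval and exact test are kept on this route. The SAP provided covers safety data only (SAP section 2, Overview) and adds nothing here.

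On sample size, Protocol section 6.2.1 plans for "The sample size of n = 13 (Groups 5-6) and n=9 for each of Groups 7 and 8" after the first vaccination. After the second, "the sample sizes of n=4, 5 for Groups 7-8 will be used".

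**The concern.** The route meant to protect the answer when data are missing is less robust than the one it replaces. If every observed participant in an arm responds, the logistic likelihood keeps rising as the arm's log odds goes to infinity, so no maximum exists. Software still prints a very large coefficient with an enormous standard error, and a Wald p-value near 1. Each added covariate gives separation another way to occur.

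Even without separation, maximum-likelihood log odds ratios are biased away from zero in small samples when the model is correct. The statement about unbiased estimation therefore does not hold for response rates at these sizes.

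At stake is a prespecified analysis that could give no usable interval for a clear difference, and a remedy chosen only after the problem has been seen in the data. Table 6-3 itself lists 4/4 and 9/9 among its illustrative outcomes.

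**Working it through.** **1. The plan's own boundary figures.** The chance of no responders in an arm of n is (1 − p)^n. At p = 10%, 0.9^9 = 38.7% and 0.9^10 = 34.9%, as in Table 6-1. The score interval for 9/9 is 70.1% to 100%, as in Table 6-3. Both reproduce.

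**2. Does the fallback apply?** Inputs are the planned numbers in section 6.2.1 and the enrolment summary after the title page: "Group 7 enrolled 10 participants, 5 of whom received 2 vaccinations". Group 8 enrolled 9, of whom 6 had two doses.
- After dose 1, Groups 7-8: 18 of 19 observed; 1/19 = 5.3% missing.
- After dose 2, among those dosed twice: 4 + 5 = 9 of 11 observed; 2/11 = 18.2% missing.
- Primary timepoint (2 weeks after last vaccination), Part B: at most 1 + 2 = 3 of 29; 10.3% missing.
- After dose 2, if all enrolled in Groups 7-8 are the denominator: 10/19 = 52.6% missing.

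Only the last exceeds 20%. In Groups 7-8, more than 20% of 19 means at least 4 missing, leaving about 7 or 8 per arm.

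**3. What happens at the boundary.** Take 7/7 versus 4/7, arm as the only covariate, logit link.
- Maximum likelihood: the arm coefficient is 11.3, 26.3 and 35.3 after 10, 25 and 50 iterations. Its standard error goes from 74 to 1.3 × 10^7. There is no finite estimate.
- Fitted rates stay at 100% and 57.1%.
- Likelihood ratio: log-likelihood 4 ln(4/7) + 3 ln(3/7) = −4.780 with arm, and 11 ln(11/14) + 3 ln(3/14) = −7.274 without. The statistic is 2 × 2.494 = 4.99, p = 0.026. Fisher gives p = 0.19.
- Firth: with arm only, the fitted rate is (x + 0.5)/(n + 1). The log odds ratio is ln(7.5/0.5) − ln(4.5/3.5) = 2.46, with a finite profile interval (−0.18 to 7.45) and penalised-likelihood-ratio p = 0.070.

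**4. How often an arm is all-or-none.** Per arm, b = p^n + (1 − p)^n. For at least one of two arms, 1 − (1 − b1)(1 − b2). Example: n = 7, p = 80% gives b = 21.0%, and 1 − 0.790² = 38%. True rates are assumed, and results are the same for p and 1 − p.

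| Observed per arm | 50% | 70% | 80% | 90% |
|---|---|---|---|---|
| 9 and 9 | 1% | 8% | 25% | 62% |
| 7 and 7 | 3% | 16% | 38% | 73% |
| 4 and 5 | 18% | 38% | 60% | 86% |

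Covariates raise this. In simulation (1,000 runs per setting, covariates unrelated to outcome, true rate 80%), any separation with 7 per arm was 38%, 54% and 71% with zero, one and three covariates. With 4 and 5 per arm it was 62%, 78% and 93%.

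**5. Operating characteristics.** Exact enumeration over all two-arm tables, two-sided 0.05, no covariates, separated tables counted as not significant for Wald.

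| | Power, 95% vs 30%: 7 per arm | 9 per arm | Type I error, 30% vs 30%: 7 per arm | 9 per arm |
|---|---|---|---|---|
| ML, Wald | 16% | 23% | 1.6% | 1.0% |
| ML, likelihood ratio | 86% | 93% | 7.5% | 7.7% |
| Fisher | 54% | 80% | 0.7% | 1.6% |
| Firth, penalised likelihood ratio | 79% | 86% | 3.7% | 3.2% |

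**The case against.** The strongest reply is that the rule may never be used for the primary endpoint. Section 6.1 bases the immunogenicity calculations on available samples, and those counts leave 5.3%, 18.2% and at most 10.3% missing. The exact tests and score intervals then apply. This stands. A reader might infer that the primary comparison of Groups 7 and 8 is already compromised, but the documents do not support that unless participants never given a second dose count as missing, and section 6.2.1 does not use that denominator.

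A reader might also infer that 9/9 versus 3/9 would be reported as showing no difference. That does not follow. With 9 observed in each of Groups 7 and 8, the exact-test route normally applies (Fisher p = 0.009). Wald inference is also an assumption, because the plan says only that the fit is by maximum likelihood. A likelihood-ratio test stays finite, and the profile interval is unbounded on one side only. What remains is that this test exceeds its nominal level at these sizes and that the plan selects none of these options.

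Nor can the trigger be argued from Day 98 visits falling after research collection stopped on 13 March 2023. Day 98 is not the primary timepoint, and Group 8 has no Day 98 visit.

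Two further limits stand. The covariates are the available baseline predictors of the missing outcomes, not every baseline variable. Section 6.5.4.1 also leaves some test choices to a SAP, and an immunogenicity SAP, if there is one, was not available to check.

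**Conclusion.** The point holds as a gap in a prespecified contingency. If the fallback is used with a logit link and an arm is all-or-none, the plan yields no finite odds ratio or Wald interval. The surviving likelihood-ratio test has about 7.5% type I error at 30% versus 30% with 7 to 9 per arm.

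How likely this is depends on true response rates that the documents do not state. With 7 per arm it is rare near 50% (3%) and usual near 90% or 10% (73%). It is more frequent with 4 and 5 per arm or with covariates. The result rests on the logit link, on independent binary responses and, for the operating characteristics, on a model with arm only.

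The rule would matter for endpoints or timepoints with more missing data than the primary one, or after dose 2 if all 19 enrolled in Groups 7-8 form the denominator. It is worth correcting because the change is small and is best made before results are seen.

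**What to change.** In the paragraph of section 6.5.4.1 on more than 20% missing:
- State the logit link, and fit the response-rate model by Firth penalised likelihood, with penalised-likelihood-ratio tests and profile intervals.
- Say that the score interval and the Barnard or Fisher test from the same section are reported alongside.
- Remove the claim of unbiased estimation for response rates.
- State the denominator for the 20% rule after dose 2: those dosed twice or all enrolled.

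Keep the baseline predictors of missingness. Cutting the model to arm and randomisation stratum would reduce separation but would also remove the support for the missing-at-random assumption, which is why the fallback exists.

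The cost is protocol or SAP wording; standard SAS and R procedures fit this model. The statistical price is slight shrinkage of rates towards 50%. With 7 per arm and arm only, 7/7 is fitted as 7.5/8 = 93.8% and 4/7 as 4.5/8 = 56.3% instead of 57.1%. Reporting crude rates with score intervals alongside keeps that visible.
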